17. PUBLICATION AND DATA SHARING POLICY

The results of this study may be published or presented at scientific meetings.

Any publication or communication (oral or written) will be defined by mutual agreement between the investigators according to international guidelines. All the authors who participated actively to the conception of the study, its development and writing of results will be cited, i.e :

- The principal investigator, the co-investigator, and all investigators who have included and followed patients.
- The contributors of the coordinating centre team who participated in the drafting of the protocol and the statistical analysis of the study.

The Luxembourg Institute of Health will be cited as a sponsor of the clinical study.

18. FUTURE USE OF STORED SPECIMENS AND DATA

Sample and Data will be stored and used for future research projects, respecting the choices of the participants mentioned in the Informed Consent signed during the inclusion visit.

19. PROTOCOL DEVIATION

In case a subject is transferred outside Luxembourg during the course of the study, the samples and data will not be collected during the time of this transfer. The subjects will however be maintained in the study and will be given the possibility to resume his/her participation in the study once back in Luxembourg.

Annex 2 : **QUESTIONNAIRES** de suivi à distance des patients positifs

Utilisation du module ePRO de l’outil Ennov Clinical Questionnaires français V1.0

ETAPES

1. Envoi par mail de liens vers les questionnaires
2. Remplissage par le participant depuis un smartphone, tablette ou ordinateur :
 - 1 questionnaire chaque jour pendant 14j
 - 1 questionnaire par semaine pendant les semaines 3 et 4
 - 1 questionnaire par mois de M2 à M12
 - Des questionnaires permanents à remplir dès que possible après l’inclusion

Table des matières

[Questionnaire J0-J14](#)

[Questionnaires courts Fin de semaine 3 et Fin de semaine 4.](#)

[Questionnaires Mensuels \(2-12 mois\)](#)

[Questionnaires permanents](#)

[Profil](#)

[Traitements actuels \(hors traitements liés à Covid19\)](#)

[Tabac](#)

[Activité physique](#)

[Alimentation](#)

Questionnaire J0-J14

Mon état de santé général

Dans le cadre de votre suivi à domicile pendant 14j, veuillez remplir ce questionnaire de suivi quotidien.

1) Vous êtes:

Si A l'hôpital : Lequel : menu déroulant

2) Comment vous sentez-vous aujourd'hui ?

3) Avez-vous bien dormi ?

Si non, pourquoi ?

4) Avez-vous une toux sèche ?

5) Avez-vous une augmentation de votre toux habituelle ces derniers jours ?

6) Avez-vous un mal de gorge apparu ces derniers jours ?

7) Avez-vous noté une forte diminution ou perte de votre goût ou de votre odorat ?

8) Avez-vous de la diarrhée ? Avec au moins 3 selles molles par jour.

9) Avez-vous des douleurs musculaires ou des courbatures inhabituelles ces derniers jours ?

10) Avez-vous des douleurs thoraciques ces derniers jours ?

11) Quel est votre niveau de douleur actuel ? (Notez de 1 à 10)

12) Avez-vous de la fièvre ?

13) Avez-vous un thermomètre ?

Si oui, Veuillez prendre votre température : si > ou = 38°C

14) Avez-vous des difficultés respiratoires ?

15) Avez-vous vu apparaître une gêne respiratoire ou une augmentation de votre gêne respiratoire habituelle ?

16) Quel est votre poids (kg) ? (se peser sans chaussure)

17) Avez-vous des difficultés importantes pour vous alimenter ou boire ?

18) Avez-vous d'autres symptômes ?

Si oui, veuillez préciser lesquels :

Les personnes de votre entourage

Pour éviter la contamination de votre entourage,

19) Avez-vous eu un contact proche avec des personnes de votre entourage aujourd'hui ?

20) Avez-vous noté une apparition subite d'éruptions cutanées au niveau des mains ou des pieds (par exemple engelures, rougeurs persistantes parfois douloureuses, lésions d'urticaire passagères) ?

[figure not shown]
21) Avez-vous noté l'apparition d'une conjonctivite ou de douleurs dans les yeux (rougeurs persistantes au niveau du blanc de l'œil, démangeaisons au niveau des paupières, sensations de picotements, brûlure, larmolement fréquent) ?

Mon état de santé général

Dans le cadre de votre suivi à domicile, veuillez remplir ce questionnaire de suivi hebdomadaire.

- 1) Comment vous sentez-vous aujourd’hui ? Je me sens bien / Je me sens fatigué(e) / Je me sens mal
- 2) Dans l’ensemble, vous pensez que votre santé est : Excellente / très bonne / bonne / médiocre / mauvaise
- 3) Vous sentez-vous plein d’énergie ? Oui / Non
- 4) Avez-vous bien dormi ? Oui/Non
- 5) Fatigue

- Une valeur basse indique que l’affirmation ne s’applique pas tout à fait ou pas du tout
- Une valeur élevée indique que l’affirmation s’applique fortement à votre état ou à ce que vous avez ressenti au cours de la semaine passée.

| Durant la semaine dernière j’ai trouvé que: | | SCORE | | | | | | |
|---|--|----------------------------|----------------------------|----------------------------|----------------------------|----------------------------|----------------------------|----------------------------|
| FSS1 | Je me sens moins motivé du fait de la fatigue |  1 |  2 |  3 |  4 |  5 |  6 |  7 |
| FSS2 | L'exercice physique est pour moi source de fatigue |  1 |  2 |  3 |  4 |  5 |  6 |  7 |
| FSS3 | Je suis facilement fatigué(e) |  1 |  2 |  3 |  4 |  5 |  6 |  7 |
| FSS4 | La fatigue interfère avec mon activité physique |  1 |  2 |  3 |  4 |  5 |  6 |  7 |
| FSS5 | La fatigue est souvent un problème pour moi |  1 |  2 |  3 |  4 |  5 |  6 |  7 |
| FSS6 | Ma fatigue m’empêche de réaliser des tâches physiques soutenues et prolongées |  1 |  2 |  3 |  4 |  5 |  6 |  7 |
| FSS7 | La fatigue interfère avec mes facultés pour la réalisation de certaines activités et responsabilités |  1 |  2 |  3 |  4 |  5 |  6 |  7 |
| FSS8 | La fatigue fait partie des mes 3 symptômes les plus gênants |  1 |  2 |  3 |  4 |  5 |  6 |  7 |
| FSS9 | La fatigue interfère avec mon travail, ma famille ou ma vie sociale |  1 |  2 |  3 |  4 |  5 |  6 |  7 |

SCORE GLOBAL : moyenne des 9 questions

5) Qualité de vie respiratoire

Les phrases suivantes expriment des sentiments sur les conséquences de votre maladie respiratoire. Pour chacune, cochez l’intensité qui vous correspond le mieux maintenant. Aucune réponse n’est juste, elle est avant tout personnelle.

| | | Pas du tout | Un peu | Moyennement | Beaucoup | Extrêmement |
|----|---|--------------------------|--------------------------|--------------------------|--------------------------|--------------------------|
| 1 | Je souffre de mon essoufflement |  |  |  |  |  |
| 2 | Je me fais du souci pour mon état respiratoire |  |  |  |  |  |
| 3 | Je me sens incompris(e) par mon entourage |  |  |  |  |  |
| 4 | Mon état respiratoire m'empêche de me déplacer comme je le voudrais |  |  |  |  |  |
| 5 | Je suis somnolent(e) dans la journée |  |  |  |  |  |
| 6 | Je me sens incapable de réaliser mes projets |  |  |  |  |  |
| 7 | Je me fatigue rapidement dans les activités de la vie quotidienne |  |  |  |  |  |
| 8 | Physiquement, je suis insatisfait(e) de ce que je peux faire |  |  |  |  |  |
| 9 | Ma maladie respiratoire perturbe ma vie sociale |  |  |  |  |  |
| 10 | Je me sens triste |  |  |  |  |  |
| 11 | Mon état respiratoire limite ma vie affective |  |  |  |  |  |

Questionnaires Mensuels (2-11 mois)

Mon état de santé général

Dans le cadre de votre suivi, veuillez remplir ce questionnaire de suivi.

- 1) Comment vous sentez-vous aujourd'hui ? Je me sens bien / Je me sens fatigué(e) / Je me sens mal.
- 2) Sommeil, échelle PSQI

1/ Au cours du mois dernier, quand êtes-vous habituellement allé vous coucher le soir ?

➤ Heure habituelle du coucher :

2/ Au cours du mois dernier, combien vous a-t-il habituellement fallu de temps (en minutes) pour vous endormir chaque soir ?

➤ Nombre de minutes :

3/ Au cours du mois dernier, quand vous êtes-vous habituellement levé le matin ?

➤ Heure habituelle du lever :

4/ Au cours du mois dernier, combien d'heures de sommeil effectif avez-vous eu chaque nuit ?

(Ce nombre peut être différent du nombre d'heures que vous avez passé au lit)

➤ Heures de sommeil par nuit :

- 3) Depuis le remplissage de votre dernier questionnaire, avez-vous consulté pour une raison en lien avec Covid19 ? Oui/Non
-> si oui, pour quel motif ? (Champ libre)

- 4) Votre qualité de vie (Echelle SF 12)

1. Dans l'ensemble, pensez-vous que votre santé est :

- 1 Excellente 2 Très bonne 3 Bonne 4 Médiocre 5 Mauvaise

2. En raison de votre état de santé actuel, êtes-vous limité pour :

- des efforts physiques modérés (déplacer une table, passer l'aspirateur, jouer aux boules...)?
 1 Oui, beaucoup limité 2 Oui, un peu limité 3 Non, pas du tout limité
- monter plusieurs étages par l'escalier ?
 1 Oui, beaucoup limité 2 Oui, un peu limité 3 Non, pas du tout limité

3. Au cours de ces 4 dernières semaines, et en raison de votre état physique :

- avez-vous accompli moins de choses que vous auriez souhaité ?
 1 Toujours 2 La plupart du temps 3 Souvent 4 Parfois 5 Jamais
- avez-vous été limité pour faire certaines choses ?
 1 Toujours 2 La plupart du temps 3 Souvent 4 Parfois 5 Jamais

4. Au cours de ces 4 dernières semaines, et en raison de votre état émotionnel (comme vous sentir triste, nerveux ou déprimé) :

- avez-vous accompli moins de choses que vous auriez souhaité ?
 1 Toujours 2 La plupart du temps 3 Souvent 4 Parfois 5 Jamais
- avez-vous eu des difficultés à faire ce que vous aviez à faire avec autant de soin et d'attention que d'habitude ?
 1 Toujours 2 La plupart du temps 3 Souvent 4 Parfois 5 Jamais

5. Au cours de ces 4 dernières semaines, dans quelle mesure vos douleurs physiques vous ont -elles limité dans votre travail ou vos activités domestiques ?

- 1 Pas du tout 2 Un petit peu 3 Moyennement 4 Beaucoup 5 Enormément

6. Les questions qui suivent portent sur comment vous vous êtes senti au cours de ces 4 dernières semaines. Pour chaque question, indiquez la réponse qui vous semble la plus appropriée.

- y a-t-il eu des moments où vous vous êtes senti calme et détendu ?
 1 Toujours 2 La plupart du temps 3 Souvent 4 Parfois 5 Jamais
- y a-t-il eu des moments où vous vous êtes senti débordant d'énergie ?
 1 Toujours 2 La plupart du temps 3 Souvent 4 Parfois 5 Jamais
- y a-t-il eu des moments où vous vous êtes senti triste et abattu ?
 1 Toujours 2 La plupart du temps 3 Souvent 4 Parfois 5 Jamais

7. Au cours de ces 4 dernières semaines, y a-t-il eu des moments où votre état de santé physique ou émotionnel vous a gêné dans votre vie sociale et vos relations avec les autres, votre famille, vos amis, vos connaissances ?

- 1 Toujours 2 La plupart du temps 3 Souvent 4 Parfois 5 Jamais

5) Qualité de vie respiratoire (Echelle VQ11)

| | | Pas du tout | Un peu | Moyennement | Beaucoup | Extrêmement |
|----|---|--------------------------|--------------------------|--------------------------|--------------------------|--------------------------|
| 1 | Je souffre de mon essoufflement |  |  |  |  |  |
| 2 | Je me fais du souci pour mon état respiratoire |  |  |  |  |  |
| 3 | Je me sens incompris(e) par mon entourage |  |  |  |  |  |
| 4 | Mon état respiratoire m'empêche de me déplacer comme je le voudrais |  |  |  |  |  |
| 5 | Je suis somnolent(e) dans la journée |  |  |  |  |  |
| 6 | Je me sens incapable de réaliser mes projets |  |  |  |  |  |
| 7 | Je me fatigue rapidement dans les activités de la vie quotidienne |  |  |  |  |  |
| 8 | Physiquement, je suis insatisfait(e) de ce que je peux faire |  |  |  |  |  |
| 9 | Ma maladie respiratoire perturbe ma vie sociale |  |  |  |  |  |
| 10 | Je me sens triste |  |  |  |  |  |
| 11 | Mon état respiratoire limite ma vie affective |  |  |  |  |  |

- 6) Avez-vous repris un rythme de vie comparable à celui que vous aviez avant la survenue des premiers symptômes associés à Covid19 ? Oui/Non
-> Si non, pourquoi ? Champ Libre
- 7) Avez-vous repris votre activité professionnelle normalement ? Oui/Non/Je suis à la retraite ou sans emploi
-> Si non, avez-vous été arrêté des suites de complications du Covid19 ? Oui/Non
- 8) Depuis le diagnostic de Covid19 ou la survenue de symptômes associés à Covid19, est-ce que vos relations avec votre entourage (famille, amis) : Se sont Dégradées / Sont Restées les mêmes / Se sont améliorées
-> si Dégradées ou Améliorées : Pourquoi ? Champ Libre
- 9) Par rapport à avant votre diagnostic à Covid19 ou vos symptômes associés à Covid19, diriez-vous aujourd'hui que :
- Votre appétit
 - Votre activité physique
 - Votre sommeil
- (Réponses : A diminué / Est identique ou quasiment identique / A augmenté)

Questionnaires permanents

A remplir une seule fois sur l'application pendant le suivi

Profil

- J'accepte que mes données collectées dans le cadre de mon suivi à distance puissent être utilisées à des fins de recherche (Oui/Non)
-
- Pays de naissance
-
- Etes-vous propriétaire de votre logement ? oui/non
- Quelle est la superficie de votre logement ?
 - Moins de 30 m²
 - 30-60m²
 - 60-90 m²
 - 90-120m²
 - 120m² - 150m²
 - Plus de 150m²
- Combien de personnes vivent dans le même foyer que vous ?
 - Adultes (18 ans et plus) : __
 - Adolescents (14 ans et 18 ans) : __
 - Enfants (13 ans et moins) : __
- Quel est le revenu annuel de votre foyer ?
 - Moins de 750 €/mois (soit moins que 9000 €/an)
 - 750 à 1499 €/mois (soit 9000 à 17999 €/an)
 - 1500 à 2249 €/mois (soit 18000 à 26999 €/an)
 - 2250 à 2999 €/mois (soit 27000 à 35999 €/an)
 - 3000 à 4999 €/mois (soit 36000 à 59999 €/an)
 - 5000 à 10000 €/mois (soit 60000 à 119999 €/an)
 - Plus que 10000 €/mois (or more than 120000 €/an)
- Quel est votre niveau d'éducation le plus élevé ?
 - Enseignement primaire
 - Premier cycle de l'enseignement secondaire (p.ex. 5e secondaire général, 9e régime technique, 9e régime préparatoire modulaire, 9e de la 2e voie de qualification)
 - Deuxième cycle de l'enseignement secondaire (p.ex. diplôme de fin d'études secondaires, diplôme de fin d'études secondaires techniques, diplôme de technicien, diplôme de fin d'apprentissage (CCP, DAP, CITP, CCM, CATP))
 - Enseignement postsecondaire non tertiaire (p.ex. Brevet de Maîtrise)
 - Enseignement supérieur ; cycle court d'études supérieures à orientation pratique, technique ou professionnelle après la fin de l'enseignement secondaire (p.ex. BTS)
 - Enseignement supérieur; niveau licence ou équivalent (p.ex. Bachelor)
 - Enseignement supérieur; niveau Master ou équivalent (p.ex. Master, ancienne licence ou diplôme universitaire d'au moins 4 ans)
 - Enseignement supérieur; niveau doctorat ou équivalent (PhD)

- Exercez-vous actuellement une activité professionnelle ? oui/non
 - Si non, pourquoi ? préretraite retraite chômage invalidité autre
- Quelle est votre profession ou la dernière profession que vous avez exercée ?
 - Agriculteur exploitant
 - Artisan, commerçant ou chef d'entreprise
 - Cadre ou profession intellectuelle supérieure
 - Profession libérale
 - Profession intermédiaire
 - Employé
 - Ouvrier (y compris ouvrier agricole)

Activité physique

- Avez-vous pratiqué une activité physique intense durant les 10 jours qui ont précédé les premiers symptômes liés à Covid19 ? (Oui/Non/Je ne sais pas)
 - Si oui, laquelle ? : Champ libre
- Quand vous répondez aux questions suivantes, merci de décrire votre pratique d'activité physique habituelle sur l'année passée, à savoir celle que vous pratiquiez habituellement avant les premiers symptômes liés à Covid19. Cette année, combien d'heures avez-vous consacré en moyenne par semaine (indiquez le nombre d'heures pleines en moyenne, Ex. Aucune=0, 2h15=2, 2h30=3)

| Activité Physique | En hiver | En été |
|---|----------|--------|
| À la marche (y compris pour aller au travail, faire des courses, pour vos loisirs...) | __ h | __ h |
| A faire du vélo (y compris pour aller au travail, pour vos loisirs...) | __ h | __ h |
| Au jardinage et/ou bricolage | __ h | __ h |
| Aux tâches ménagères (cuisine, ménage,...) | __ h | __ h |
| Au sport (natation, gymnastique, tennis, | __ h | __ h |

- En moyenne, avant les premiers symptômes liés à Covid19, combien d'heures par jours restiez-vous assis (au travail, pendant les repas, devant un écran, à lire etc...) __ h

Alimentation

- Avant les premiers symptômes liés à Covid19, à quelle fréquence consommiez-vous habituellement les aliments ou boissons suivants, quel que soit leur mode de conservation (frais, en conserve ou surgelé), le moment de consommation (repas ou hors repas) et le lieu (domicile ou hors domicile) ?

| Aliments | Jamais ou presque | Moins d'une fois par semaine | Environ 1 fois par semaine | 2 à 3 fois par semaine | 4 à 6 fois par semaine | 1 fois par jour ou plus. Dans ce cas, combien de fois ou d'unités par jour |
|----------|-------------------|------------------------------|----------------------------|------------------------|------------------------|--|
| | | | | | | |

| | | | | | | |
|---|--|--|--|--|--|------|
| Fruits et légumes | | | | | | --/j |
| Pains, céréales, pommes de terre et légumineuses | | | | | | --/j |
| Produits complets | | | | | | --/j |
| Lait & produits laitiers | | | | | | --/j |
| Charcuterie et viande transformée | | | | | | --/j |
| Viandes, volaille, produits de la mer, œufs | | | | | | |
| Produits de la mer | | | | | | --/j |
| Matières grasses ajoutées | | | | | | --/j |
| Type de matières grasses | | | | | | --/j |
| Produits sucrés | | | | | | --/j |
| Boissons non alcoolisées | | | | | | --/j |
| Boissons alcoolisées | | | | | | |
| Sel | | | | | | |

- Avant les premiers symptômes liés à Covid19, prenez-vous régulièrement des compléments alimentaires ou vitamines riches en :
 - Vitamine D (oui/non)
 - Vitamine C (oui/non)
 - Zinc (oui/non)
 - Fer (oui/non)
 - Magnésium (oui/non)
 - Multivitamines (oui/non)
 - Autres (oui/non)

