2.2 Rationale

The pathogen for the new outbreak has been identified as a novel enveloped RNA betacoronavirus2 that has currently been named severe acute respiratory syndrome coronavirus 2 (SARS-CoV-2), which has a phylogenetic similarity to SARS-CoV (1). Studies on epidemiological and clinical characteristics of patients with COVID-19 show that compared to women, men are more infected and the median age is 49.0 years (1, 4). Common symptoms at onset of illness are fever, cough, dyspnoea and myalgia or fatigue; less common symptoms were sputum production, headache, haemoptysis and diarrhea. Complications included acute respiratory distress syndrome, anaemia, acute cardiac injury and secondary infection (4). The risk for serious disease and death in COVID-19 cases increases with age (5). In the United States case-fatality percentages increased with increasing age, from no deaths reported among persons aged ≤ 19 years to highest percentages (10%–27%) among adults aged ≥ 85 years (5). The findings from the United States are similar to data from China, which indicated $>80\%$ of deaths occurred among persons aged ≥ 60 years (5). As of 19 March 2020, no vaccine has been successfully developed for COVID-19. The treatments are mainly symptomatic and supportive. The study by Huang et al. reported that the most common complications in patients with 2019-nCoV infection were acute respiratory distress syndrome, followed by anemia, acute heart injuries, and secondary infections.

Due to the rapid spread of COVID-19, we determined that identifying profiles of patients predictive of more severe prognosis would be key to clinical management and would support more efficient public health measures. Although there have been some studies on epidemiological and clinical characteristics of patients with COVID-19, there is a lack of research investigating the prognostic factors for the severity of the disease. The accurate prognostic evaluation of COVID-19 can provide a guiding basis for active and effective management of the outbreak.

The purpose of this project is the identification of patients clinical and socio-demographic characteristics as well as pathogen and/or host predictive biomarkers for the severity of the disease. We are aiming to better understand the heterogeneity observed in disease severity through a stratification approach of the cohort in Luxembourg.

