| VIH/SIDA | • O U I | • N O N | • N / A | | | | |

Hypertension

COPD

Maladie inflammatoire chronique (ex: syndrome du côlon irritable)

DEBUT DE SYMPTOMES & ADMISSION

Date du premier symptôme : [] [] [] / [] [] [] / [2] [0] [] [] []

Date d'admission dans l'établissement : [] [] [] / [] [] [] / [2] [0] [] [] []

Heure d'admission (Format 24 heures) : [] [] [] [] / [] [] [] []

Transfert depuis un autre établissement de santé ? OUI, d'un autre centre participant OUI, d'un centre non participant

- NON N/A

Si OUI : Nom de l'établissement d'origine : __ N/A

Si OUI : Date d'admission dans l'établissement d'origine (JJ/MM/AAAA) :

[] [] [] / [] [] [] / [2] [0] [] [] [A] N/A

Si OUI, il s'agit d'un autre centre participant : Numéro d'identification d'origine du patient

: Inchangé Différent : [] [] [] - [] [] [] [] N/A

Antécédent de voyage dans les 14 jours précédant la survenue des premiers symptômes ? OUI NON NC

Si OUI, localisation géographique et dates du séjour : Pays

: __ Ville ou zone géographique : __

Date de retour : [] [] [] / [] [] [] / [2] [0] [] [] [] N/A (espace supplémentaire à la fin du document si besoin) Contact avec des animaux, consommation de viande crue, piqûre d'insecte dans les 14 jours précédant la survenue des symptômes ?

- OUI NON NC N/A Si OUI, compléter la section EXPOSITION ANIMALE

SECTION PRINCIPALE

SIGNES ET SYMPTÔMES A L'ADMISSION (Données disponibles dès l'admission – dans les 24 premières heures)

Température : [] [] [] . [] °C FC : [] [] [] battements/min FR : [] [] respiration/min

PAS : [] [] [] mmHg PAD : [] [] [] mmHg Déshydratation sévère : OUI NON NC

Temps de recoloration cutanée (sternum) >2 secondes : OUI NON NC

Saturation en oxygène : [] [] [] % Sous air ambiant : OUI NON N/A ou

Oxygénothérapie : OUI NON

- N/A

SIGNES ET SYMPTÔMES A L'ADMISSION (observés/reportés à l'admission et associés à l'événement en cours)

Antécédents de fièvre

- OUI
- NON
- NC

Toux

- OUI
- NON
- NC

Expectorations associées

- OUI
- NON
- NC

Hémoptysie associée

- OUI
- NON
- NC

| | | | |
|--|-------|-------|------|
| Maux de gorge | • OUI | • NON | • NC |
| Rhinorrhée | • OUI | • NON | • NC |
| Otalgie | • OUI | • NON | • NC |
| Sifflement | • OUI | • NON | • NC |
| Douleur thoracique | • OUI | • NON | • NC |
| Myalgies | • OUI | • NON | • NC |
| Arthralgies | • OUI | • NON | • NC |
| Fatigue / Malaise | • OUI | • NON | • NC |
| Dyspnée | • OUI | • NON | • NC |
| Tirage sous-costal | • OUI | • NON | • NC |

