ANNEX 5 :

QUESTIONNAIRE PREDI-COVID-H

Utilisation du module e-PRO de Ennov Clinical

Questionnaires français

V1.0

Suivi à distance depuis un smartphone, tablette ou ordinateur :

- 1 questionnaire court par jour tant qu'il n'y a pas eu de confirmation de Covid19 par test positif et pendant 14 jours

Table des matières

[Système d'alerte](#)

[Questionnaire quotidien](#)

[Questionnaire permanent](#)

[Profil](#)

Questionnaire quotidien

Mon état de santé général

Vous êtes un membre du foyer d'une personne diagnostiqué positif à Covid19. Veuillez remplir ce questionnaire de suivi quotidien.

1) Date du questionnaire :

2) Avez-vous été testé et diagnostiqué positif à Covid19 ? Oui/Non

3) Vous êtes: A la maison / A l'hôpital / Autre

Si A l'hôpital : Lequel : menu déroulant

Centre Hospitalier de Luxembourg / Fondation Hôpitaux Robert Schuman / Centre Hospitalier Emile Mayrisch / Centre Hospitalier du Nord / Autre

4) Comment vous sentez-vous aujourd'hui ? Je me sens bien / Je me sens fatigué(e) / Je me sens mal

5) Avez-vous bien dormi ? Oui/Non

Si non, pourquoi ? [Champ libre]

6) Avez-vous une toux sèche ? Oui/Non

7) Avez-vous une augmentation de votre toux habituelle ces derniers jours ? Oui/Non

8) Avez-vous un mal de gorge apparu ces derniers jours ? Oui/Non

9) Avez-vous noté une forte diminution ou perte de votre goût ou de votre odorat ? Oui/Non

10) Avez-vous de la diarrhée ? Avec au moins 3 selles liquides/molles par jour. Oui/Non

11) Avez-vous des douleurs musculaires ou des courbatures inhabituelles ces derniers jours ? Oui/Non

12) Avez-vous des douleurs thoraciques ces derniers jours ? Oui/Non

13) Quel est votre niveau de douleur actuel ? (Notez de 1 à 10)

14) Avez-vous de la fièvre ? Oui/Non

Avez-vous un thermomètre ? Oui/ Non

Si oui, Veuillez prendre votre température :

15) Avez-vous des difficultés respiratoires ? Oui/Non

16) Avez-vous vu apparaître une gêne respiratoire ou une augmentation de votre gêne respiratoire habituelle ? Oui/Non

17) Quel est votre poids ? (se peser sans chaussure) __ kg ou Je ne sais pas

18) Avez-vous des difficultés importantes pour vous alimenter ou boire ? Oui/Non

19) Avez-vous d'autres symptômes ? Oui/Non

Si oui, veuillez préciser lesquels : [champ libre]

Questionnaire permanent

A ne remplir qu'une fois

Profil

-
- Sexe
- Date de naissance
- Poids (kg)
- Avant le diagnostic de Covid19, avez-vous perdu, sans le vouloir, 3 kg ou plus dans les 6 derniers mois ? (Oui/non)
- Taille (cm)

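### The daily symptom forms have no structured item for a productive cough, so cough at home can be under-recorded and a change from dry to productive cough cannot be told from resolution on the dry-cough item

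*Protocol*

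**What the plan says.** Annex 2, Questionnaire J0-J14, has two structured cough items. Item 4 asks "Avez-vous une toux sèche" and item 5 asks "Avez-vous une augmentation de votre toux habituelle ces derniers jours". Item 18 is open: "Avez-vous d'autres symptômes", followed by "Si oui, veuillez préciser lesquels". The household form in Annex 5 has the same pair as items 6 and 7 (item 6 reads "Avez-vous une toux sèche ? Oui/Non") and the same open question as item 19.

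The ISARIC-based CRF in Annex 3 treats cough differently. Its list of signs and symptoms at admission has a general cough item (*Toux*) and a separate one, "Expectorations associées". The schedule in section 7.1 has the CRF data collected daily for hospitalised patients but once, at baseline, for patients at home.

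Section 2.2 names cough among the common onset symptoms and adds that "less common symptoms were sputum production, headache, haemoptysis and diarrhea". Section 3.2 makes the description of symptom trajectories after diagnosis a secondary objective. Sections 3.1 and 11.4 plan to group patients by disease course and trajectory.

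**The concern.** The two structured items do not cover all coughs between them. One requires the cough to be dry. The other requires a usual cough that has increased. A new productive cough meets neither condition, although the protocol itself lists sputum production as a symptom.

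The gap bears on change over time as well as on presence. If a cough changes type during the 14 days of daily follow-up, the dry-cough item can go from Oui to Non while the participant is still coughing. An analyst who read that series as a cough trajectory would date the end of the cough too early. What is at stake is the accuracy of one of the main symptoms in a descriptive secondary objective, and of any cluster that takes daily cough as an input.

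**Working it through.** No arithmetic applies. The check traces truthful answers through the items and then asks whether another instrument fills the gap.

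**1. Answers on the daily form**

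| Participant's true state | Item 4 (dry) | Item 5 (usual cough increased) | Where it is recorded |
|---|---|---|---|
| No usual cough, new dry cough | Oui | Non | Item 4 |
| Usual cough, now worse and productive | Non | Oui | Item 5 |
| No usual cough, new productive cough | Non | Non | Free text only |
| No usual cough, dry cough that turns productive | Oui, then Non | Non (Oui if *habituelle* is read loosely) | Item 4 until the change, then free text only |
| No usual cough, dry cough that ends | Oui, then Non | Non | Item 4 until it ends |

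The third row is the missing presence. The fourth and fifth rows give the same sequence on item 4, and on item 5 too unless the participant stretches the word for usual. The structured items therefore cannot separate a change of type from resolution.

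**2. Comparison within the same form.** For breathlessness, item 15 of the J0-J14 form covers both new onset and an increase over the usual level. Item 5 on cough has only the increase. The form already contains the pattern that would have closed the gap.

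**3. Other instruments**

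- CRF: the general cough and sputum items sit in the admission section. For patients at home they are completed once (section 7.1), so they cannot correct later days. The daily section of the CRF, as shown in Annex 3, has no cough item.
- Week 3, week 4 and monthly forms, as shown in Annex 2: they ask about breathlessness and respiratory quality of life, but not about cough.
- Free text (item 18, or item 19 in the household form): it can hold a productive cough, but only if the participant thinks to add it after two cough questions, and does so again each day.

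For patients at home, items 4 and 5 are therefore the only structured daily cough series in the annexes.

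**4. Pooling.** Section 10 plans to recode all sources to a single codebook. CRF *Toux* means any cough and item 4 means dry cough. Placing both under one variable would mix two definitions.

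**5. Size.** Among coughing participants, the part missed on the structured items is the productive coughs that are not reported as an increase of a usual cough. Free text recovers some of these. The documents give none of these shares. The loss lies between nothing (every such cough written in) and the whole of that share (none written in).

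**The case against.** The best reply is that item 4 says dry cough and records exactly that. The protocol sets no scoring rule for items 4 and 5 and no recovery definition that uses them, so nothing in it counts a Non as no cough or as recovery. Every daily form has free text, and item 5 may be answered Oui by someone who reads it broadly. This stands, and it limits the point to a missing item and an ambiguity in later use. It does not remove the gap, because unprompted text is not equivalent to a Yes/No question.

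A reader might infer that the link between cough and severity is weakened or even reversed. The documents do not support that. They say nothing about the productive share by severity. The CRF gives both hospitalised and home patients a baseline any-cough variable that items 4 and 5 do not touch. The criteria in section 4.1 do not name cough.

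A reader might also infer that CRF and daily data cannot be used together. That goes too far: CRF cough without sputum approximates dry cough and can be set beside item 4.

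Finally, the rash question, "Avez-vous noté une apparition subite d'éruptions cutanées au niveau des mains ou des pieds", may look like the same fault, since the CRF asks about rash without a site. It is a targeted question about lesions of the hands and feet, with its own examples. Widening it would be a preference, not a correction.

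**Conclusion.** The point holds in a limited form. Neither daily form has a structured item for a new productive cough, and on item 4 (item 6 in the household form) a change from dry to productive cough cannot be told from the cough ending. For patients at home no other structured instrument shown in the annexes repairs this after baseline.

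The consequence is possible under-recording of cough, and possible misdating of its end, in the secondary objective on symptom trajectories and in clustering that uses them. The main criteria of section 4.1 and the comparison of baseline cough with severity are not affected. The size cannot be derived from the documents.

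The conclusion assumes that participants answer the two items literally and that the annexes show the forms in use. The detailed questionnaires for months 12, 15 and 24 are not reproduced there, but they come too late to bear on the daily series.

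**What to change.** Keep items 4 and 5 (items 6 and 7 in Annex 5) unchanged so that the series stays comparable. Add one item to both forms: *Avez-vous une toux grasse (avec crachats) aujourd'hui ? Oui/Non*. Define any cough as Oui to any of the three. Adding is better than replacing: a replacement would break the series, and a question about a new cough is unclear on a daily form, where a cough that began a week earlier may no longer count as new.

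For forms collected before the change:

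- set a form-version flag;
- report item 4 as dry cough;
- do not count a change to Non as the end of cough;
- code productive cough from the free text where it is given;
- do not merge item 4 with CRF *Toux* as one variable in the codebook.

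The cost is one more question per day and a small ePRO change. Earlier forms keep the narrower definition. Any cough will also include an unchanged usual productive cough, as item 4 already includes a usual dry one. The rules for forms already collected need no new data and can be adopted even if the forms are not reissued.
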